15.5 Intraocular Pressure (IOP)

Intraocular pressure (IOP) will be assessed in both eyes by Goldman applanation tonometry at each visit. Results will be taken from a single measurement and will be recorded in mmHg.

The IOP values and changes from baseline for each eye (study eye and non-study eye) will be summarized using descriptive statistics (number of observations, mean, SD, median, minimum, and maximum values) by visit and eye for each treatment group and for all patients combined. In addition, the proportion of patients with an increase in IOP ≥10 mm Hg from baseline and the proportion of patients with an IOP ≥30 mm Hg at the visit will be presented using frequency counts and percentages. A patient listing of IOP will also be produced.

16. Interim Analyses

There are no planned interim analyses.

17. Changes from Protocol-Stated Analyses

The imputation methodology for the Per Protocol population, described in Section 9.2 of this SAP, differs from that described in the Protocol. The SAP accurately reflects how data will be handled for patients who are discontinued from study treatment due to lack of efficacy.

18. Reporting Conventions

Reporting conventions will adhere when possible to the International Conference on Harmonization (ICH) Guidance E3, "Structure and Content of Clinical Study Reports". All tables and listings will be presented in landscape format. All SAS output for tables and listings will be distributed in PDF files.

19. Revisions History

Documentation of revision to the SAP will commence after approval of the Final version 1.0.

Statistical Analysis Plan Protocol RTA 408-C-1307

Version 307 1.0

20. Tables

Table		Population
Number	Title	Intent-to-Treat
14.1.1	Summary of Analysis Populations, All Patients	Intent-to-Treat
14.2.2.1	Patient Disposition	
14.1.2.2	Patient Disposition	Per Protocol
14.1.3	Significant Protocol Deviations	Safety
14.1.4.1	Demographic Characteristics	Safety
14.1.4.2	Demographic Characteristics	Intent-to-Treat
14.1.4.3	Demographic Characteristics	Per Protocol
14.1.5.1	Non-Ocular Medical History	Intent-to-Treat
14.1.5.2	Ocular Medical History	Intent-to-Treat
14.1.6.1	Non-Ocular Prior and Concomitant Medication Use, Classified by WHO ATC Drug Classification	Intent-to-Treat
14.1.6.2	Ocular Prior and Concomitant Medication Use, Classified by WHO ATC Drug Classification	Intent-to-Treat
14.2.1.1	Absence of Anterior Chamber Cells at Day 15 and Ocular Pain at Day 4, Last Observation Carried Forward	Intent-to-Treat
14.2.1.2	Absence of Anterior Chamber Cells at Day 15 and Ocular Pain at Day 4, Observed Data	Intent-to-Treat
14.2.1.3	Absence of Anterior Chamber Cells at Day 15 and Ocular Pain at Day 4, Missing Data Imputed as Failures	Intent-to-Treat
14.2.1.4	Absence of Anterior Chamber Cells at Day 15 and Ocular Pain at Day 4, Observed Data	Per Protocol
14.2.2.1	Absence of Anterior Chamber Cells by Visit	Intent-to-Treat
14.2.2.2	Absence of Anterior Chamber Flare by Visit	Intent-to-Treat
14.2.2.3	Absence of Anterior Chamber Cells and Flare by Visit	Intent-to-Treat
14.2.2.4	Absence of Ocular Pain by Visit	Intent-to-Treat
14.2.3.1	Anterior Chamber Cells Grade by Visit	Intent-to-Treat
14.2.3.1	Anterior Chamber Ceas Grade by Visit Anterior Chamber Flare Grade by Visit	Intent-to-Treat
14.2.3.2	Sum of Anterior Chamber Cells and Flare Grades by Visit	Intent-to-Treat
14.2.3.4	Ocular Pain Score by Visit	Intent-to-Treat
	Summary of Treatment Emergent Adverse Events	Safety
14.3.1.1	Treatment-Emergent Adverse Events by System Organ Class	Safety
14.3.1.2		Safety
14.3.1.3	Treatment-Emergent Adverse Events by System Organ Class and	
14.3.1.4	Relationship to Study Drug	Cofoty
14.3.1.5	Serious Treatment-Emergent Adverse Events by System Organ Class	Safety
14.3.1.6	Treatment-Emergent Adverse Events Leading to Patient Discontinuation by System Organ Class	Safety
14.3.2.1.1	Slit Lamp Biomicroscopy Findings	Safety
14.3.2.1.2	Slit Lamp Biomicroscopy Findings – Shift Table	Safety
14.3.2.2.1	Dilated Indirect Ophthalmoscopic Examination Findings Safe	
14.3.2.2.2	Dilated Indirect Ophthalmoscopic Examination Findings – Shift Table	Safety

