Summaries for continuous variables will include the sample size (n), mean, standard deviation, median, minimum, and maximum. Summaries for discrete variables will include frequencies and percentages. Differences between treatment groups will be calculated as Test – Placebo and change from baseline will be calculated as follow-up visit – baseline. The baseline visit will be defined as the last non-missing measure prior to initiation of investigational treatment. All efficacy analyses will use a one-sided alpha=0.10 test unless otherwise stated.
The secondary efficacy variables, study eyes with absence of anterior chamber cells (Visits 3, 4 or 6), study eyes with absence of pain (Visits 4, 5 or 6) and study eyes with absence of flare (Visits 3, 4, 5 or 6) will be summarized similarly to the primary efficacy summaries. Additionally, anterior chamber cells and flare as well as pain at each visit and change from

	baseline will be summarized using continuous and discrete summary statistics.
	The sum of anterior chamber cells and flare grade will be summarized similarly to anterior chamber cells and flare separately.
	Safety Analysis:
	The primary safety analysis will summarize ocular treatment emergent AEs (TEAEs) in the study eye for all treated patients using discrete summaries at the patient and event level by system organ class and preferred term for each treatment group. A TEAE will be defined as any AE that occurs after the treatment is initiated. An additional analysis will examine ocular AEs for the non-study eye. Non- ocular TEAEs will be summarized using discrete summaries at the patient and event level by system organ class and preferred term for each treatment group. Treatment related ocular and non-ocular TEAEs will be summarized similarly. Ocular and non-ocular TEAEs will also be summarized by severity.
	The IOP data will be summarized at each visit using both continuous summaries (including change from baseline) and discrete summaries (including the proportion of patients with change in IOP from baseline ≥ 10 mm Hg and the proportion of patients with an IOP ≥ 30 mm Hg that occurs at any time following initiation of study treatment) as well as shift tables.
	Slit lamp biomicroscopy and dilated indirect ophthalmoscopic examination measures will be summarized at each visit using discrete summary statistics.

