10.12 Safety Analyses

The primary safety analysis will summarize ocular treatment-emergent AEs (TEAEs) in the study eye for all treated patients using discrete summaries at the patient- and event-level by system organ class and preferred term for each treatment group. A TEAE will be defined as occurring on or after the day that treatment is initiated. An additional analysis will investigate ocular AEs for the non-study eye. Non-ocular TEAEs will be summarized using discrete summaries at the patient- and event-level by system organ class and preferred term for each treatment group. Treatment-related ocular and non-ocular TEAEs will be summarized similarly. Ocular and non-ocular TEAEs will also be summarized by severity.

The IOP data will be summarized at each visit using both continuous summaries (including change from baseline) and discrete summaries (including the proportion of patients with change in IOP from baseline ≥ 10 mm Hg and the proportion of patients with an IOP ≥ 30 mm Hg that occurs at any time following instillation of study treatment) as well as shift tables.

Slit lamp biomicroscopy and dilated indirect ophthalmoscopic examination measures will be summarized at each visit using discrete summary statistics.

Visual acuity data will be summarized at each visit, using discrete summaries, including change from baseline in the number of lines and the proportion of patients with change from previous visit of ≥ 2 lines.

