6.4 Unscheduled Visits

Unscheduled data, such as information from unscheduled visits or Investigator comments, will be included in the data listings. In general, these data will be excluded from the summary tables unless otherwise specified.

7. Study Design and Procedures

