15.2 Slit-Lamp Biomicroscopy

A slit-lamp biomicroscopy examination of the cornea, conjunctiva, anterior chamber, iris, lens, and lid will be performed for both eyes at each visit. The results will be graded as normal, abnormal not clinically significant (NCS) or abnormal clinically significant (CS).

The results will be summarized using counts and percentages for each treatment group and for all patients combined at each visit for each eye (study eye and non-study eye). Percentages will be based on the number of patients in each treatment group with responses. Shift tables for the slit-lamp biomicroscopy parameters will also be provided comparing each follow-up visit to baseline (Visit 2 [Day 1]). A patient listing of the slit-lamp biomicroscopy parameters will also be produced.

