14.3.2.3 Pin-Hole Visual Acuity Safety		

Statistical Analysis Plan Protocol RTA 408-C-1307

307 1.0

Version

Table Number	Title	Population
14.3.2.4	Intraocular Pressure (IOP)	Safety
14.3.3	Treatment Exposure	Safety
14.3.4	Dosing Compliance	Safety

21. Listings

Listing Number	Title	Population
16.1.7	Randomization Schedule	Intent-to-Treat
16.2.1.1	Patient Disposition and Informed Consent	Intent-to-Treat
16.2.1.2	Inclusion/Exclusion Criteria	Intent-to-Treat
16.2.2	Protocol Deviations	Intent-to-Treat
16.2.3	Patients Excluded from Study Populations	Intent-to-Treat
16.2.4.1	Demographics	Intent-to-Treat
16.2.4.2	Medical History	Intent-to-Treat
16.2.4.3	Prior and Concomitant Medications	Safety
16.2.5	Study Drug Dosing Compliance and Exposure	Intent-to-Treat
16.2.6.1	Ocular Inflammation Assessment of Anterior Chamber Cell and Flare	Intent-to-Treat
16.2.6.2	Ocular Pain Assessment	Intent-to-Treat
16.2.7.1	All Adverse Events	Safety
16.2.7.2	Adverse Events Leading to Treatment Discontinuation	Safety
16.2.7.3	Serious Adverse Events	Safety
16.2.8	Pregnancy Test Results	Safety
16.3.2.1	Intraocular Pressure (IOP)	Safety
16.3.2.2	Slit Lamp Biomicroscopy	Safety
16.3.2.3	Pin-Hole Visual Acuity (ETDRS)	Safety
16.3.2.4	Dilated Indirect Ophthalmoscopic Examination	Safety

22. Figures

Figure Number	Title	Population
14.2.1.1	Absence of Anterior Chamber Cells at Each Visit	Intent-to-Treat
14.2.1.2	Absence of Ocular Pain at Each Visit	Intent-to-Treat
14.2.2.1	Anterior Chamber Cells at Each Visit	Intent-to-Treat
14.2.2.2	Ocular Pain at Each Visit	Intent-to-Treat

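### SAP 15.5 replaces the protocol's any-time proportion with IOP of 30 mm Hg or more by a by-visit one and plans no IOP shift table, and SAP 17 declares neither change

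*SAP*

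**What the plan says.** **Protocol.** The Safety Analysis part of the synopsis and section 10.12 each describe the IOP summaries in one long sentence. In 10.12 it opens: "The IOP data will be summarized at each visit using both continuous summaries". It then lists the discrete summaries. The item for IOP of 30 mm Hg or more carries its own time qualifier. In the synopsis it is an elevation "that occurs at any time following initiation of study treatment) as well as shift tables"; in 10.12 it is one "that occurs at any time following instillation of study treatment) as well as shift tables". The item for a 10 mm Hg change from baseline has no such qualifier.

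**SAP.** Section 15.5 plans descriptive statistics by visit and eye, the proportion with a rise of at least 10 mm Hg, and a patient listing. For the threshold it says that the "proportion of patients with an IOP ≥30 mm Hg at the visit will be presented using frequency counts and percentages". It names no shift table. The table list in SAP 20 has a single IOP entry, Table 14.3.2.4, and SAP 21 has Listing 16.3.2.1. SAP 17, which records changes from the protocol's analyses, declares only the Per Protocol imputation method.

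**Unscheduled readings.** Protocol 8.4.2 includes IOP among the evaluations that may be done at an unscheduled visit. SAP 6.4 puts unscheduled data in the listings and adds: "In general, these data will be excluded from the summary tables unless otherwise specified". SAP 15.5 specifies no exception.

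**The concern.** A programmer who follows the SAP exactly will not produce two safety displays that the protocol specifies, and nothing in the SAP tells the reader that they were dropped.

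The any-time proportion answers a patient-level question: how many patients in each arm ever reached 30 mm Hg after dosing began. By-visit proportions answer a different one: how many were at or above that level on a given day. The second does not yield the first unless high readings are confined to one visit. The shift table answers a third question, namely where each patient moved relative to baseline, which by-visit means and maxima do not show.

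IOP is a named safety measure, and the synopsis describes this as the first clinical study of the ophthalmic suspension. The safety readout is descriptive, so which descriptive tables exist matters.

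**Working it through.** **Step 1: texts side by side.**

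| Item | Protocol synopsis and 10.12 | SAP 15.5 and SAP 20 | Declared in SAP 17? |
|---|---|---|---|
| IOP of 30 mm Hg or more | Any time after treatment starts | At each visit | No |
| IOP shift tables | Required | None in 15.5; one IOP table (14.3.2.4), not labelled as a shift table | No |

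The mismatch is not a leftover from an amendment. Protocol Amendment 1 is dated 10 February 2014, and its summary of changes has no entry for section 10.12. The SAP pages carry the date 13 February 2014.

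**Step 2: what by-visit rows can and cannot tell.** Neither document gives an IOP event rate, so there is no plan figure to reproduce. The counts below are assumed; they show what is possible, not what is expected.

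Inputs:
- n = 35 patients per arm (Protocol sections 4 and 5.1), assuming that all are dosed, so that all are in the Safety population, and that all are measured at every visit.
- Four scheduled post-dose visits, 3 to 6 (Protocol 8.3.1 and Appendix 2). The Visit 2 reading is the baseline (SAP 6).
- m_v = number of patients at or above 30 mm Hg at visit v, for one eye.

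Formula: the any-time count A over scheduled visits satisfies max(m_v) ≤ A ≤ min(n, sum of m_v). The lower bound is reached when the same patients recur, the upper when all are different.

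| Patients at or above 30 mm Hg at Visits 3, 4, 5, 6 | Any-time count | Any-time proportion |
|---|---|---|
| 0, 0, 0, 0 | 0 | 0% |
| 1, 0, 0, 0 | 1 | 1/35 = 2.9% |
| 2, 0, 0, 0 | 2 | 2/35 = 5.7% |
| 1, 1, 0, 0 | 1 to 2 | 2.9% to 5.7% |
| 1, 1, 1, 0 | 1 to 3 | 2.9% to 3/35 = 8.6% |
| 1, 1, 1, 1 | 1 to 4 | 2.9% to 4/35 = 11.4% |

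With at most one non-zero row, the any-time count over scheduled visits is fixed. Once two or more rows are non-zero, it generally is not. In the last line every row shows 2.9%, whether one patient stayed high throughout or four patients each crossed once.

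**Step 3: unscheduled visits.** Under the SAP 6.4 default, a patient whose only crossing is at an unscheduled visit adds 1/35 = 2.9 percentage points to the any-time proportion and nothing to any planned row. Early-exit readings are recorded on the Visit 6 pages (Protocol 8.4.2), so this affects only genuinely unscheduled visits. The documents give no frequency for those.

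**The case against.** **The protocol sentence is mixed.** It opens with by-visit summaries, so the time qualifier could be read as merely restricting the item to post-dose readings, tabulated by visit. That reading is available but weaker. The qualifier is attached to the 30 mm Hg item alone, in both places, and has little work to do unless the item is cumulative. It also cannot explain the missing shift table, which is named separately.

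**Nothing is lost, and substitutes exist.** This stands. Every reading is in the database and in Listing 16.3.2.1, and with about 35 patients per arm the any-time count could be taken from the listing by hand. By-visit maximum IOP, rises of at least 10 mm Hg, ocular adverse events by eye (SAP 15.1) and study-eye concomitant medications (SAP 12.2) give partial views. None is the per-arm proportion or the shift from baseline that the protocol names.

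**Stronger readings that the documents do not support.**
- A reader might infer that IOP was singled out, because SAP 15.2 says that shift tables for the slit-lamp "biomicroscopy parameters will also be provided comparing each follow-up visit to baseline" and SAP 20 lists "Dilated Indirect Ophthalmoscopic Examination Findings – Shift Table". But pin-hole visual acuity has no shift table either (SAP 15.4, Table 14.3.2.3). The SAP plans shift tables for the two examinations graded normal or abnormal, not for the two numeric measures. The protocol also defines no IOP categories, so its shift table could not be programmed from the protocol alone.
- A reader might infer that SAP 6.4 contradicts SAP 9.3, which says that no Safety-population data are excluded. The two can be read together: 9.3 defines a population, while 6.4 sets a table default and keeps the data in listings. The gap is only that 15.5 makes no exception.
- A reader might take the percentages above as a forecast, or as evidence of bias between arms. The counts are assumed, and nothing in the documents points to a difference between arms.

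**Conclusion.** The concern holds as an undeclared departure from the protocol in a descriptive safety output. Two items are affected: the any-time proportion at or above 30 mm Hg, replaced by a by-visit one, and the IOP shift table, absent.

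The practical size is conditional. If crossings are absent or confined to one scheduled visit, the by-visit rows already give the scheduled-visit answer. If they fall at several visits, the rows leave a range, up to 2.9% to 11.4% in the assumed case of one patient per visit at four visits with 35 per arm. Crossings seen only at unscheduled visits enter no summary row under the SAP 6.4 default.

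Efficacy inference is unaffected, and the results are untabulated rather than lost. The change should be made because the protocol specifies these outputs and the correction is small.

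**What to change.** 1. **Any-time row.** In SAP 15.5 and Table 14.3.2.4, add the number and percentage of patients with IOP of 30 mm Hg or more at any post-dose assessment, scheduled or unscheduled. Present it by arm, separately for the study eye and the non-study eye, on the Safety population. Naming the eye matters, because a row defined only per patient could pool the two. Keep the by-visit rows.
2. **Unscheduled readings.** State in 15.5 that this row is an exception to SAP 6.4. That section already allows exceptions, so its own text need not change.
3. **Shift table.** Add the IOP shift table to 15.5 and to the table list, with categories that the sponsor fixes before unmasking. Otherwise, declare and justify its omission in SAP 17.

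The cost is one row per eye, one sentence, and either one table with its category definitions or a short SAP 17 entry. The data are already collected, and no visit or procedure changes.

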14.3.2.3 Pin-Hole Visual Acuity Safety		

Statistical Analysis Plan Protocol RTA 408-C-1307

307 1.0

Version

Table Number	Title	Population
14.3.2.4	Intraocular Pressure (IOP)	Safety
14.3.3	Treatment Exposure	Safety
14.3.4	Dosing Compliance	Safety

21. Listings

Listing Number	Title	Population
16.1.7	Randomization Schedule	Intent-to-Treat
16.2.1.1	Patient Disposition and Informed Consent	Intent-to-Treat
16.2.1.2	Inclusion/Exclusion Criteria	Intent-to-Treat
16.2.2	Protocol Deviations	Intent-to-Treat
16.2.3	Patients Excluded from Study Populations	Intent-to-Treat
16.2.4.1	Demographics	Intent-to-Treat
16.2.4.2	Medical History	Intent-to-Treat
16.2.4.3	Prior and Concomitant Medications	Safety
16.2.5	Study Drug Dosing Compliance and Exposure	Intent-to-Treat
16.2.6.1	Ocular Inflammation Assessment of Anterior Chamber Cell and Flare	Intent-to-Treat
16.2.6.2	Ocular Pain Assessment	Intent-to-Treat
16.2.7.1	All Adverse Events	Safety
16.2.7.2	Adverse Events Leading to Treatment Discontinuation	Safety
16.2.7.3	Serious Adverse Events	Safety
16.2.8	Pregnancy Test Results	Safety
16.3.2.1	Intraocular Pressure (IOP)	Safety
16.3.2.2	Slit Lamp Biomicroscopy	Safety
16.3.2.3	Pin-Hole Visual Acuity (ETDRS)	Safety
16.3.2.4	Dilated Indirect Ophthalmoscopic Examination	Safety

22. Figures

Figure Number	Title	Population
14.2.1.1	Absence of Anterior Chamber Cells at Each Visit	Intent-to-Treat
14.2.1.2	Absence of Ocular Pain at Each Visit	Intent-to-Treat
14.2.2.1	Anterior Chamber Cells at Each Visit	Intent-to-Treat
14.2.2.2	Ocular Pain at Each Visit	Intent-to-Treat
